9.2.1 Eligibility

9.2.1.1 Inclusion Criteria

- 1. Subjects must be 18 to 40 years old on the date the ICF is signed and have the capacity to provide voluntary informed consent.
- 2. Subjects must be able to read, understand, and provide written informed consent on the IRB-approved ICF and provide authorization as appropriate for local privacy regulations.
- 3. Subjects must have clear central corneas and be free of any anterior segment disorders in each eye.
- 4. Subjects must be myopic, require contact lens correction from -1.00 diopter (D) to -6.00 D, and wear contact lenses in each eye.
- 5. Subjects must be correctable through spherocylindrical refraction to 47 letters (0.0 logarithm of the minimum angle of resolution [logMAR]) or better (distance, high-contrast) in each eye.
- 6. Subjects must be able and willing to comply with all treatment and follow-up/study procedures.
- 7. Subjects must be adapted soft contact lens wearers and agree to wear their study lenses on a daily wear basis for approximately 3 months.

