9.2.1.2 Exclusion Criteria

- 1. Subjects participating in any drug or device clinical investigation within 2 weeks prior to entry into this study and/or during the period of study participation.
- 2. Subjects who are women of childbearing potential (those who are not surgically sterilized or postmenopausal) are excluded from participation in the investigation if they meet any one of the following conditions:

- She is currently pregnant.
- She plans to become pregnant during the study.
- She is breastfeeding.
- 3. Subjects who have worn gas permeable lenses in either eye within the last 30 days or who have worn polymethylmethacrylate lenses in either eye within the last 3 months.
- 4. Subjects with any systemic disease currently affecting ocular health or which in the Investigator's opinion may have an effect on ocular health in either eye during the course of the study.
- 5. Subjects using any systemic or topical medications that will, in the Investigator's opinion, affect ocular physiology or lens performance.
- 6. Subjects with an active ocular disease in either eye or who are using any ocular medication.
- 7. Subjects who currently wear monovision, multifocal, or toric contact lenses in either eye.
- 8. Subjects with an ocular astigmatism >1.00 D in either eye.
- 9. Subjects with anisometropia (spherical equivalent) >2.00 D.
- 10. Subjects with any Grade ≥2 finding in either eye during the slit lamp examination (refer to APPENDIX B for methods of clinical evaluation). Subjects with corneal infiltrates in either eye, of ANY GRADE, are not eligible to participate in this study.
- 11. Subjects with any "Present" finding during the slit lamp examination in either eye (refer to APPENDIX B for methods of clinical evaluation) that, in the Investigator's judgment, interferes with contact lens wear.
- 12. Subjects with any scar or neovascularization within the central 6 mm of the cornea in either eye. Subjects with minor peripheral corneal scarring (that does not extend into the central area), that in the Investigator's judgment, does not interfere with contact lens wear, are eligible to participate in this study.
- 13. Subjects who are aphakic in either eye.
- 14. Subjects who are amblyopic in either eye.
- 15. Subjects who have had any corneal surgery (eg, refractive surgery) in either eye.
- 16. Subjects who are allergic to any component in the study care products.
- 17. Subjects who meet any of the following criteria:

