12.1.1 Screening Visit (Visit 1)

NOTE: All VA measurements MUST be made using a phoropter.

A Screening Log will be provided by the Sponsor to track all consented subjects that the Investigator interviews regarding the study. Once all available lines on the Screening Log have been completed, or the Investigator has fulfilled his/her quota of subjects, the Investigator will sign and date the form to verify that all the subjects who interviewed for the study have provided informed consent and Health Insurance Portability Accountability Act (HIPAA) authorization and any other applicable state requirements. The Investigator will send a copy of the Screening Log to the Sponsor. The Investigator will retain the original document for his/her records.

After obtaining written informed consent, prospective subjects will be screened to determine whether they meet the entry criteria for the study.

Screening will proceed as follows:

- a. Enter the subject information on the next available line of the Screening Log.
- b. Collect subject's medical history
- c. Collect the following lens history information from the subject:
 - Average number of days per week worn
 - Average daily wearing time, hours per day
 - Average hours of comfortable wear per day

- Hours lenses worn on the day of this visit
- Current lens brand and lens wear modality
- Current lens care products
- d. Collect demographic and baseline information and perform the following baseline assessments (without lenses) and record in the subject's source document:
 - Spherocylindrical refraction
 - Distance best spectacle-corrected visual acuity (BSCVA)
 - Keratometry
- e. Perform a slit lamp examination (remove the lenses if the subject wore lenses to the visit). Record and diagram the results and findings in the subject's source document and appropriate eCRF:
 - Any ungraded finding marked as "Present"
 - Any corneal scars
 - Any neovascularization within the central 6 mm of the cornea
 - Any corneal staining
 - Any corneal infiltrate (record details on the Corneal Infiltrates Evaluation Form [APPENDIX C])
 - any other graded slit lamp findings Grade 2 or greater
- f. Indicate on the Screening Log whether the subject is a "Screen Pass" or "Screen Fail."
 - "Screen Fail" subjects are ineligible and cannot be randomized in the study. The reason for screen failure must be documented on the Screening Log and in the subject record and must be maintained with a copy of their ICF.

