 - Only "Screen Pass" subjects should be randomized in the study.
- g. If the subject is eligible, collect Symptoms/Complaints and Subjective Assessment information from the subject regarding their habitual lenses.
- h. Assign subject numbers based on the randomization system. The unmasked designee will determine the subject's randomized lens by using the randomization system and record on the Screening Log.
- i. Assess BSCVA to determine subject prescription. The prescription determined from this fitting assessment will be used to dispense/order test or control lenses according to the lens to which the subject is randomized.
- j. Record the lens parameters to be dispensed/ordered based on the diagnostic fitting.
- k. For each subject, use the lens order form to order the appropriate study contact lenses (test or control). Schedule the subject for their Dispensing Visit within 30 days.

- 1. Collect/assess all AEs, including serious or significant non-serious AEs, since consent was signed.
- m. For female subjects, re-emphasize the exclusion criterion stating that if the subject is of childbearing potential and is pregnant and or breast feeding, she is ineligible to be a part of the study.

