12.1.2 Dispensing Visit (Visit 2)

- a. Collect/assess all AEs, including serious or significant non-serious AEs.
- b. Perform a slit lamp examination (remove the lenses if the subject wore lenses to the visit). Record all slit lamp findings and, at a minimum, sketch the following in the subject's source document:
 - any ungraded finding marked as "PRESENT"
 - any new corneal scars
 - any neovascularization within the central 6 mm of the cornea
 - any corneal staining
 - any corneal infiltrate (record details on the Corneal Infiltrates Evaluation Form [APPENDIX C])
 - any other graded slit lamp findings Grade 2 or greater
- c. Dispense study lens, record sphere power, record in Product Accountability Log. In an effort to ensure that both the Investigator and subject remain masked, the unmasked designee MUST dispense the study lenses and MUST remove lenses from their glass vials out of the Investigator's and subject's sight immediately prior to dispensing.
- d. Subject inserts pair of the study lenses in his/her eyes.

NOTE: Study lenses should be allowed to equilibrate a minimum of 3 minutes on the eye.

- e. After a minimum of 3 minutes, perform the following assessments:
 - Collect Symptoms/Complaints and Subjective Assessment information
 - Distance high-contrast logMAR lens VA
 - Over-refraction and distance VA
 - Lens wettability, centration, movement
 - Lens deposits

For each eye, compare the distance high-contrast logMAR lens VA to the distance BSCVA obtained at the Screening visit. If the VA has decreased by ≥5 letters (0.1 logMAR), explain.

- f. Dispense lens case. Instruct the subject to store their study lenses in the lens case filled with Bausch + Lomb Biotrue MPS according to the Subject Instructions (APPENDIX D).
- g. If the subject is discontinued or exited at this visit, complete the Exit Visit eCRF.

- h. For female subjects, re-emphasize the exclusion criterion stating that if the subject is of childbearing potential and is pregnant and or breast feeding, she is ineligible to be a part of the study.
- 12.1.3 1-Week, 1-Month, 2-Month, and 3-Month Visits (Visits 3, 4, 5, and 6)
- NOTE: All VA measurements MUST be made using a phoropter.
- NOTE: If all scheduled visits are performed on time and the subject completed the 3-Month Visit, the Exit Visit will be done at the same time.

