- NOTE: Study lenses should not be dispensed at this visit unless replacement lenses are required. Lenses worn to this visit should be returned to the subject for use until the next scheduled visit.
- NOTE: If the subject does not come to a visit wearing lenses due to requiring a replacement and is not experiencing any problems, it is preferred to do an Unscheduled Visit for Product Dispensing Only and reschedule the current visit within the visit window. Refer to Unscheduled Visit, Section 12.1.4.
 - a. Collect/assess all AEs, including serious or significant non-serious AEs.
 - b. Collect the following lens information from the subject:
 - Average number of days per week worn
 - Average daily wearing time, hours per day
 - Average hours of comfortable wear per day
 - Hours lenses worn on the day of this visit
 - c. Collect Symptoms/Complaints and Subjective Assessment information from the subject regarding their study lenses.
 - d. Evaluate the lenses (while on eye), and record the following assessments:
 - Distance high-contrast logMAR lens VA
 - Over-refraction and distance VA
 - Lens wettability, centration, movement
 - Lens deposits

For each eye, compare:

- The distance high-contrast logMAR lens VA at this visit to the distance high-contrast logMAR lens VA obtained at the Dispensing Visit.
- The distance high-contrast logMAR lens VA at this visit to the distance BSCVA obtained at the Screening Visit
- If the VA has decreased by ≥ 10 letters (0.2 logMAR), explain.
- e. Perform a slit lamp examination (remove the lenses if the subject wore lenses to the visit) and note the following:
 - Any ungraded finding marked as "Present"
 - Any new corneal scars
 - Any neovascularization within the central 6 mm of the cornea
 - Any corneal staining

- Any corneal infiltrate (record details on the Corneal Infiltrates Evaluation Form – APPENDIX C)
- Any other graded slit lamp findings Grade >2
- f. For female subjects, re-emphasize the exclusion criterion stating that if the subject is of childbearing potential and is pregnant and or breast feeding, she is ineligible to be a part of the study.

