14.4.1 Primary Effectiveness Endpoint

When the sample sizes in the groups are 100 eyes and 50 eyes, a 2-group 0.05 one-sided t-test will have 99% power to reject the null hypothesis that the test lens is inferior to the Clinical Study Protocol

control lens (the difference in means, μ_T - μ_C , is ≥ 0.060) in favor of the alternative hypothesis that the test lens is non-inferior to the control lens, assuming that the expected difference in means is 0.000 and the common SD is 0.076.

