14.7.1.2 Primary Effectiveness Analysis

Monocular distance high-contrast logMAR lens VA will be assessed at each scheduled visit (Dispensing Visit and 1-Week, 1-Month, 2-Month, and 3-Month Visits). VA will be converted to logMAR units. For each eye, logMAR VA will be averaged over all scheduled visits resulting in 1 value of "All Study" logMAR lens VA per eye.

"All Study" logMAR lens VA will be presented using continuous summary statistics for the PP population by treatment group in a table at the eye level. A 2-sided 90% confidence interval for the difference (test – control) in "All Study" logMAR lens VA will be constructed using an analysis of variance (ANOVA) model with fixed factors of treatment and site. If the upper limit of the confidence interval is \leq 0.06 then the null hypothesis will be rejected and the test lens will be statistically successful in this outcome.

The previous analysis will also be completed using the ITT Population as a sensitivity analysis. For this sensitivity analysis, missing logMAR VA values will be imputed 25

times using the Markov chain Monte Carlo (MCMC) method. The seed used to generate the imputations will be 1187871241. The results of analyses (as described above for the PP population) by imputation will be combined to produce a 2-sided 90% confidence interval for the difference between treatments.

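### The primary lens VA model omits pre-randomisation Screening BSCVA; this is not an error, but prespecifying it costs one degree of freedom and would probably sharpen the comparison

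*Combined protocol and SAP*

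**What the plan says.** Section 14.7.1.2 averages each eye's logMAR lens VA over the Dispensing, 1-Week, 1-Month, 2-Month and 3-Month Visits. It then builds a 2-sided 90% confidence interval for test minus control "using an analysis of variance (ANOVA) model with fixed factors of treatment and site". The upper limit is compared with 0.06. No baseline measure enters the model. The same analysis is repeated in the ITT population after 25 MCMC imputations, and the variables in the imputation model are not listed.

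Section 12.1.1 collects distance BSCVA at step d, among the baseline assessments without lenses. Randomisation follows at step h. Step i then says "Assess BSCVA to determine subject prescription", so Screening lists BSCVA twice, once on each side of randomisation.

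The protocol already treats Screening BSCVA as the per-eye reference for lens VA. At dispensing (12.1.2): "For each eye, compare the distance high-contrast logMAR lens VA to the distance BSCVA obtained at the Screening visit". At each follow-up visit (12.1.3) sites compare "The distance high-contrast logMAR lens VA at this visit to the distance BSCVA obtained at the Screening Visit". These are site-level checks and do not feed the primary analysis.

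Section 14.5 stratifies randomisation by site only. Section 14.7 defers a full declaration to a separate SAP, but 14.7.1.2 already names the model terms.

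**The concern.** If an eye's best corrected acuity predicts how well it sees through a study lens, a model without it leaves explainable variation in the residual, and the interval compared with 0.06 is wider than it needs to be. Any chance imbalance in baseline acuity also stays in the estimate. That is the same loss seen another way, not a second harm, because the planned interval already allows for chance imbalance.

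Precision and power are at stake, not validity. The timing matters as well: a covariate named before unmasking is prespecified, while the same covariate added afterwards is a post hoc choice.

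**Working it through.** **Inputs from the plan.** Eyes: 100 test and 50 control; one-sided alpha 0.05; "assuming that the expected difference in means is 0.000 and the common SD is 0.076" (all 14.4.1). Margin 0.06 (14.1.1). Sites: 7 to 10 (9.1).

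**Assumed.** Eight sites. r is the correlation between step d BSCVA and All Study lens VA within treatment and site; it is not in the documents, so 0 to 0.7 is shown. Eyes are taken as independent, as the plan does, until the last two steps.

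**1. The plan's own power.** SE = 0.076 × √(1/100 + 1/50) = 0.01316. The noncentral t with 148 df and noncentrality 0.06/0.01316 = 4.56 gives power 0.998. The stated 99% reproduces.

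**2. The planned interval.** With treatment and eight sites, df = 150 − 1 − 8 = 141. Half-width = 1.6557 × 0.01316 = 0.0218 logMAR.

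**3. Adding BSCVA.** df falls to 140. Adjusted SE = SE × √[(1 − r²)(1 + 1/139)], where the last factor is the expected penalty for chance imbalance in the covariate. Width ratio = √[(1 − r²)(1 + 1/139)] × t(0.95; 140)/t(0.95; 141). Power is from the noncentral t.

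| r | Change in width | Half-width | Power, true difference 0 | Power, true difference 0.02 |
|---|---|---|---|---|
| Planned model | – | 0.0218 | 99.8% | 91.6% |
| 0 | +0.4% | 0.0219 | 99.8% | 91.4% |
| 0.1 | −0.1% | 0.0218 | 99.8% | 91.7% |
| 0.2 | −1.7% | 0.0214 | 99.9% | 92.4% |
| 0.3 | −4.3% | 0.0209 | 99.9% | 93.5% |
| 0.5 | −13% | 0.0189 | 99.98% | 96.7% |
| 0.7 | −28% | 0.0156 | >99.99% | 99.5% |

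The true difference of 0.02 is an illustration; the plan assumes 0.

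**4. Break-even.** Setting the width ratio to 1 gives r = 0.085; with 7 or 10 sites it is 0.085 or 0.086. A simulation with 10 sites and 6,000 trials per value of r agrees: mean width ratio 1.0037 at r = 0, 1.0000 at 0.085 and 0.958 at 0.3. The threshold concerns expected width. In a single trial the adjusted interval was narrower about 41% of the time at r = 0.09 and about 98% at r = 0.3.

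**5. Counting subjects instead of eyes.** With 75 subjects and eight sites, break-even rises to r of about 0.126, and the cost at r = 0 to about 0.8%.

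**6. Does BSCVA repair the independence assumption in 14.7.1.1?** No. The planned eye-level model was simulated at a true difference of 0.06, with 50 and 25 subjects, two eyes each, eight sites, the same between-eye correlation (ICC) in BSCVA and in the residual, and 20,000 trials per cell. One-sided error over r from 0 to 0.7:

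| Assumed ICC | Without BSCVA | With BSCVA |
|---|---|---|
| 0 | 0.049–0.053 | 0.049–0.052 |
| 0.5 | 0.091–0.094 | 0.091–0.095 |
| 0.8 | 0.112–0.119 | 0.112–0.120 |

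The Monte Carlo standard error is about 0.002.

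**The case against.** The planned ANOVA is valid without the covariate, and its site term matches the stratification. On the plan's own inputs power is 99.8% with or without BSCVA, and the half-width is about a third of the margin (0.0218/0.06 = 0.36). A visible effect needs a true difference that the plan does not assume. The correlation is unknown, and the documents give reasons to expect a low one. Entry requires eyes "correctable through spherocylindrical refraction to 47 letters (0.0 logarithm of the minimum angle of resolution [logMAR]) or better", which truncates BSCVA. Only "Subjects with an ocular astigmatism >1.00 D in either eye" are excluded, so up to 1.00 D of astigmatism is corrected in the BSCVA refraction but not by the sphere-only study lenses. The 0.09 threshold is an average, rests on eye-level degrees of freedom, and narrows an interval that may already be too narrow because fellow eyes are treated as independent. The announced SAP might also hold further detail.

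Most of this stands as a limit on the size of the benefit. The 13% and 28% reductions should not be expected, since nothing in the documents supports r of 0.5 or 0.7. It is not a reason to leave BSCVA out, because the worst case is an interval 0.4% wider, or 0.8% if subjects are counted. Nor does the 99.8% settle the matter, because it relies on independent eyes. With 75 subjects as the unit, SD 0.076 per eye, an assumed ICC of 0.5 and r taken at subject level, power at a true difference of 0.02 is about 79% unadjusted, 82% with r = 0.3 and 88% with r = 0.5. At ICC 0.8 the figures are 72%, 75% and 82%. The covariate is therefore worth more once between-eye correlation is handled. The SAP deferral is a weak answer on the analysis model, whose terms are already named; it is fairer for the imputation model.

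**Conclusion.** The point holds as a recommended improvement, not a correction. Screening BSCVA is measured before randomisation, should be available for essentially every randomised eye because eligibility depends on corrected acuity in each eye, and is already the protocol's reference for lens VA. Adding it narrows the expected interval once r exceeds about 0.09 on the plan's eye-level counting, or about 0.13 counting subjects.

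The size of the gain is uncertain because r is assumed. It is negligible for power if the lenses are truly equal and SD is 0.076. It becomes useful if the test lens is slightly worse than the control. It leaves the inflation of one-sided error from ignoring between-eye correlation where it was.

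**What to change.** In 14.7.1.2, replace the ANOVA with an ANCOVA having fixed factors treatment and site and, as a linear covariate, the same eye's distance BSCVA in logMAR.

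- Define the covariate as the step d Screening value. Do not use the step i reassessment, which is listed after randomisation, or Dispensing Visit lens VA, which is post-randomisation and part of the endpoint average.
- Use the same covariate in the ITT analysis of each imputed dataset, and name it in the MCMC imputation model.
- State how an ITT eye without a step d value will be handled.
- Keep the unadjusted ANOVA as a supportive analysis.
- Deal with between-eye correlation as a separate change.

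The cost is one degree of freedom, one more variable in each model and a short missing-value rule. No extra visit, measurement or subject is needed. The sponsor should confirm that the step d and step i values can be told apart in the data, since Appendix A shows a single Screening BSCVA.

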14.7.1.3 Primary Safety Analysis

Graded slit lamp findings will be assessed at each scheduled follow-up visit (1-Week, 1-Month, 2-Month, and 3-Month Visits) and, optionally, at unscheduled visits. Each eye will be classified with respect to having 1 or more observations with Grade >2 (Yes, No) at any follow-up visit, including unscheduled visits.

The number and percentage of eyes with findings Grade >2 at any follow-up visit will be presented for the safety population by treatment group in a table. A 2-sided 90% confidence interval for the difference (test – control) between treatment groups will be constructed using the Newcombe-Wilson score method. If the upper confidence limit $\leq 10\%$ (0.10) then the null hypothesis will be rejected and the test lens will be statistically successful in this outcome. If both treatment groups have 0 eyes with a slit lamp finding Grade >2, then the confidence interval will not be calculable, the null hypothesis will be rejected, and the test lens will be statistically successful in this outcome.

14.7.2 Multiple Comparisons

Adjustment for multiple comparisons will not be necessary because statistical success will require success in both primary endpoints.

14.7.3 Interim Analyses

No interim analyses are planned.

14.7.4 Missing Data

Missing data will be imputed for the ITT population sensitivity analysis of the primary effectiveness endpoint as described above. Unless otherwise specified, missing data will not be imputed.

15.0 DATA QUALITY ASSURANCE

15.1 Study Monitoring

Bausch + Lomb Global Clinical Operations representatives must be allowed to visit all study site locations to assess the data, quality, and study integrity in a manner consistent with applicable health authority regulations and the procedures adopted by the Bausch + Lomb Global Clinical Operations Department.

Prior to the start of the study, member(s) of the Bausch + Lomb Global Clinical Operations Department (or designees) will review the protocol, eCRF, regulatory obligations, and other material or equipment relevant to the conduct of the study with the Investigator/Sub-Investigator and relevant study site personnel.

Monitoring visits and telephone consultations will occur as necessary, or per the monitoring plan, during the course of the investigation to verify the following:

• The rights and well-being of subjects are protected.

- This clinical investigation is being conducted in accordance with 21 CFR Parts 11, 50, 54, 56, and 812. The protocol was developed with consideration of the provisions in: ISO 14155-1:2011 Clinical investigation of medical devices for human subjects Part 1: General requirements; 14155-2:2011 Part 2: Clinical investigation of medical devices for human subjects Part 2: Clinical investigational plan; ISO 11980:2012 Ophthalmic Optics Contact lenses and contact lens care products Guidance for clinical investigations; ICH GCP and applicable local regulations. The Sponsor intends to register this clinical trial with the public database https://ClinicalTrials.gov.
- The integrity of the data, including adequate study documentation.
- The facilities remain acceptable.
- The Investigator and site personnel remain qualified and able to conduct the study.
- Test article accountability

During the course of the study, if the Sponsor determines that an Investigator is not compliant with the protocol and/or applicable regulatory requirements, the Sponsor will take action to secure compliance. In addition, the Sponsor may terminate the Investigator's participation in the study if appropriate, or if the Investigator remains non-compliant despite the Sponsor's actions.

